#### 3.4.2 Autoimmune Cohort

For evaluation of pre-specified, new-onset autoimmune conditions, the cohort will be the same as the general safety cohort of Regimen Initiators (at least one dose of GARDASILTM), except that the cohort will include only males who were members of the health plan during the 12-month period prior to their first dose of GARDASILTM. This membership criterion will assist in determining whether a condition is new-onset after receipt of GARDASILTM or considered as pre-existing. A description of the autoimmune comparison population of male in the health plan who were not vaccinated with GARDASILTM is provided in Section 3.7.2.

#### 3.4.3 General Safety and Autoimmune Cohort Exclusion Criteria

As a general rule, all males vaccinated with at least one dose of GARDASILTM after the approval of the male indication in the US will be included in the study.

For the general safety cohorts, the following exclusion criteria will apply:

- any females;
- males vaccinated prior to the FDA date of licensure of GARDASILTM for males for the prevention of external genital warts (October 2009); and/or
- males who received all doses of GARDASILTM outside of the health plan.

Specific to the Regimen Completers cohort, the following additional exclusion criteria will also apply:

- any male outside the 9-26 year old age range at first dose;
- males who were not health plan members at each GARDASILTM dose;
- males who completed the 3-dose regimen of GARDASILTM over a period greater than 12 months;
- males who had less than a 28-day interval between the first and second dose;
- males who had less than 12 weeks between the second and third dose; and/or
- males who had less than 24 weeks between the first and third dose.

For the autoimmune cohort of males vaccinated with GARDASILTM, the following exclusion criteria will apply (i.e., same as for general safety plus requirement of 12 months of health plan membership prior to vaccination):

- any females;
- males vaccinated prior to the FDA date of licensure of GARDASILTM for males for the prevention of external genital warts (October 2009);
- males who received all doses of GARDASILTM outside of the health plan; and/or
- males with less than 12 months of health plan membership prior to their first dose of GARDASILTM.

#### 3.5 ACCRUAL OF STUDY SUBJECTS AND ACCRUAL TIMELINES

As specified by the FDA, accrual of study participants will continue until the earliest of:

- 1) accrual of 135,000 males in the general safety Regimen Initiators cohort;
- 2) accrual of 44,000 males in the general safety Regimen Completers cohort; or
- 3) six years after study start date (as further described in Section 3.9).

There will be no active enrollment of study subjects. Study subjects will receive  $GARDASIL^{TM}$  as part of their routine medical care.

Recipients of GARDASILTM will be identified in PPD database. Vaccination details, such as date of vaccination, are available in the electronic claims records.

#### 3.6 STUDY ENDPOINTS

#### 3.6.1 General Safety Endpoints and Risk Periods

The general safety endpoints for the Regimen Initiator and/or Completer cohorts are all health outcomes resulting in an emergency room visit or hospitalization in each of the three following time periods of interest, referred to as "risk periods":

- 1) on the date of vaccination (i.e., Day 0; Note that Day 0 health outcomes are limited to pre-specified conditions, as further described below);
- 2) on Days 1-14 after vaccination (starting at the first day after vaccination); and
- 3) on Days 1-60 after vaccination (starting at the first day after vaccination). An example of the Day 1-60 risk periods is shown in Figure 3-2.

[figure not shown]
All health outcomes resulting in an emergency room visit or hospitalization will be evaluated, including venous embolism and thrombosis. This study will assess the incidence of the health outcome as defined by the first occurrence of the health outcome in the risk period of interest for a given subject. As a result, recurrences of health outcomes in the emergency room or hospital setting with the same diagnosis within this risk period will not be addressed (see Section 4.1.1 for further details). Also, if a subject receives his next dose of GARDASILTM prior to the end of a risk period associated with a previous dose, the risk period associated with the previous dose will be truncated on the day prior to receipt of the next dose, to avoid overlapping risk periods.

Health outcome codes reported for an emergency room visit or a hospitalization during the risk (and self-comparison) periods will be identified using claims associated with the appropriate ICD-9 diagnosis codes. Within the claims database, site of medical care encounters may be identified by a combination of corresponding procedure codes and codes for site of care. For hospitalizations, claims associated with the health outcomes will be identified between the beginning and end dates of a hospitalization. ICD-9 codes associated with an emergency room encounter will also be evaluated.

Figure 3-2

## General Safety Cohorts: Example of Risk Periods and Post-Vaccination Self-Comparison Periods

(Length and timing of actual periods will vary according to number of doses received and vaccination schedule of each study subject)

\*Post-vaccination self-comparison person-time will begin 91 days after each dose, thus allowing a 60-day risk window and 30-day "washout" period after each dose. In this example, the post-vaccination self-comparison time is the combined time of month 5-6 and 9-14.

ICD-9 diagnosis codes listed in any position (primary or secondary) in the database for an emergency room visit or a hospitalization occurring during the risk (or self-comparison) periods will be included in the general safety analysis, irrespective of whether it is a new diagnosis code for the patient or corresponds to a pre-existing condition or a prior episode of the health outcome. In addition, to provide interpretation context for the SRC for the primary general safety objective, the analysis will be re-run excluding chronic pre-existing conditions. The methods and decision rules for identifying and excluding chronic pre-existing conditions will be described in the study's Data Analysis Plan. The subject would still be included in analyses of all other health outcomes for which he does not have a pre-existing condition.

To facilitate the analysis and interpretation of results, all ICD-9 diagnosis codes listed for emergency room visits and hospitalizations occurring during the risk or self-comparison periods will be grouped into pre-defined health outcome categories, using the Healthcare Cost and Utilization Project (HCUP) coding structure [5]. HCUP is a comprehensive and well-established grouping structure that offers a pre-specified hierarchical grouping of all

ICD-9 diagnosis codes into a manageable number of clinically meaningful categories. The specific HCUP categories and subcategories of interest for this study will be prespecified before any analysis is performed, with concurrence from the SRC.

For events occurring on the date of vaccination (Day 0), emergency room visits and hospitalization health outcomes of interest will be limited to pre-specified, syncope, convulsive syncope; epilepsy, convulsions; head trauma; and allergic reactions. These Day 0 health outcomes of interest were pre-specified based on consideration of temporal and biological plausibility for an association with an injection or vaccination.

Death among any study subject will also be identified for the period starting at the date of their first vaccination with GARDASILTM and ending 60 days after their last vaccination. A short narrative will be prepared by PPD investigators, after appropriate approvals, summarizing relevant information from the subject's medical history, the cause of death as available in the database, death certificate information (as available through the National Death Index), or other sources as available. This information will then be reviewed by an independent physician (i.e., not part of the study research team) to determine the cause of death. Given the lag time of up to two years in the state and national death registries, a complete accounting of deaths may require a supplemental report after the study end, to be delivered after the final study report.

### 3.6.2 Identification of Pre-specified, New-Onset Autoimmune Endpoints

Although there was no indication of an autoimmune safety signal in the clinical program or post-licensure safety data of GARDASILTM, new onset of the following conditions within 6 months after receipt of any dose of GARDASILTM will be monitored:

- (1) Rheumatologic: immune thrombocytopenia, autoimmune hemolytic anemia, systemic lupus erythematosus, rheumatoid arthritis and juvenile rheumatoid arthritis, psoriatic arthritis, ankylosing spondylitis, reactive arthritis, Crohn's disease and ulcerative colitis.
- (2) Endocrine: type 1 diabetes, Hashimoto's and Graves' disease.
- (3) Neurologic/Ophthalmologic: multiple sclerosis, acute disseminated encephalomyelitis (ADEM), other demyelinating diseases of the nervous system, Guillain-Barré syndrome, neuromyelitis optica, optic neuritis, and uveitis.

## Identification of potential new-onset cases

Potential cases will be identified from a pre-specified list of ICD-9 diagnosis codes for each of these conditions, using all possible medical encounters, including outpatient visits (since these conditions are often handled on an outpatient basis), emergency room visits, and hospitalization records. When appropriate, an expanded set of ICD-9 codes, CPT codes, laboratory codes, and/or pharmacy codes potentially indicative of these conditions will be used to increase detection sensitivity. Accounting of all potential cases will be reported. Subjects with a similar autoimmune condition identified from codes in the databases within a 1-year period prior to their first dose of GARDASIL

will be flagged, as their condition is likely a pre-existing condition, and not a new onset. Medical records from at least 2 years (when available) prior to the first dose of GARDASILTM of all suspected new-onset cases will then be retrieved for review to confirm the diagnosis of the condition and the date of disease onset. If there is clear indication in the medical record that the condition was diagnosed before the first dose of GARDASILTM, that potential case will not be included for case review. In the event that a large number of potential cases of a particular condition are identified from this algorithm, a random sample of cases may be selected for review to facilitate the case review logistics.

### Case review of potential new-onset cases

Potential new-onset cases will be reviewed by the Case Review Committees (CRC). There will be three CRCs: (1) Rheumatology; (2) Endocrinology; and (3) Neurology/Ophthalmology. The CRCs will be composed of independent physicians, masked to the GARDASILTM vaccination status of each patient. The primary responsibility of the CRCs is to review redacted medical records of suspected cases of new-onset autoimmune conditions that occur in study subjects receiving GARDASILTM during the timeframe of accrual of the general safety cohorts. The study investigators at will select the CRC members for the study. The CRC members will be physicians with expertise in the particular conditions of interest, but will be independent of the study (i.e., they will not be part of the research team running the study).

Within each of the 3 CRCs, the reviews will be conducted independently by each of the 3 reviewers. The Case Review SOP will specify procedures for reconciling disagreements between the case reviewers with respect to the diagnosis or date of symptom onset. The CRC will determine the onset date of the condition (i.e., first symptoms suggestive of the condition), based on clinical manifestations and the time sequence of medical events and diagnoses. The roles and responsibilities of the CRC, and the procedures for case review and administrative procedures of the case review process will be pre-specified in an SOP.

Based on vaccination date (unavailable to the CRC), the PPD research study team will determine if the disease onset date assigned by the CRC precedes the first dose of GARDASILTM. Subjects who are confirmed as having an onset date of an autoimmune condition before receiving their first dose of GARDASILTM will not be considered a post-vaccination new onset of that condition for this study.

#### 3.7 COMPARISON POPULATIONS

#### 3.7.1 General Safety Self-Comparison Period

For the analysis of general safety, the recipients of GARDASILTM will serve as their own "controls" for any health outcome (HCUP code category) resulting in an emergency room visit or hospitalization. For each health outcome, the incidence rate of the health outcome observed during the self-comparison period will serve as a background rate to which the incidence rate observed in the risk periods immediately following vaccination can be compared. Use of a self-comparison group reduces the potential confounding

relative to an external comparison cohort since all group members will have received the vaccine. This means that whatever characteristics (both measured and unmeasured) are associated with receipt of the vaccine will be evenly distributed among the exposed and unexposed groups.

The post-vaccination self-comparison period will start 91 days after each dose of GARDASILTM. Figure 3-2 for an example in which the ACIP vaccination schedule is followed. This allows for a 60-day risk period and a 30-day "washout" period prior to the start of up to 3 self-comparison periods, each up to 60 days in length. Details of this approached will be included in the data analysis plan.

For analyses associated with Day 0 (Secondary Objective 3) and Day 1-14 health outcomes (a sub-analysis for the Primary Objective and Secondary Objective 1), a selfcomparison period of 180 days in length would create an extremely uneven length of follow-up between the risk and comparison period and is expected to result in an imbalance of chance significant findings (i.e., more chance findings suggesting an increased risk following GARDASILTM) [6]. Therefore, an attempt will be made to balance the length of the risk periods in the analysis in the Day 0 and Day 1-14 analyses. The opportunity to have had a healthcare visit during the post-vaccination selfcomparison period will be taken into consideration. For example, a day on which a doctor visit occurred during the self-comparison period will be used for outcome assessment for Day 0 analyses. Similarly, for the Day 1-14 analyses, the self-comparison period will be 14 days following the date associated with a physician visit if such visit occurred in the relevant time period. This approach will be further detailed in the study's Data Analysis Plan and may include use of simulations or developing similar length comparison periods. The methods will be finalized prior to undertaking any statistical analysis of the data.

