#### 1. BACKGROUND AND RATIONALE

#### 1.1 BACKGROUND

GARDASILTM is Merck's quadrivalent human papillomavirus (HPV) vaccine. The vaccine was approved in 2006 by the United States (US) Food and Drug Administration (FDA) and European Medicines Agency (EMEA) for the prevention of several diseases caused by HPV types 6, 11, 16, and 18 in females. In October 2009, the US FDA approved GARDASILTM for use in boys and men, 9 through 26 years of age, for the prevention of external genital warts (condyloma acuminata) caused by HPV types 6 and 11. In December 2010, the US FDA approved GARDASILTM for use in males and females, 9 through 26 years of age, for the prevention of anal intraepithelial neoplasia (AIN) grades 1, 2, and 3 caused by HPV types 6, 11, 16, and 18, and for the prevention of anal cancer caused by HPV types 16 and 18.

GARDASILTM is an aluminum adjuvanted recombinant protein particulate (virus-like particle [VLP]) vaccine that contains 20 µg HPV 6 L1 VLP, 40 µg HPV 11 L1 VLP, 40 µg HPV 16 L1 VLP, and 20 µg HPV 18 L1 VLP, along with 225 µg of amorphous aluminum hydroxyphosphate sulfate [1]. GARDASILTM is administered intramuscularly as a 0.5-mL dose according to the following schedule: 0, 2 and 6 months.

Human papillomavirus (HPV) is a family of small DNA viruses and is the most commonly detected sexually transmitted virus in men and women [2]. In men, HPV anogenital infection can result in anogenital diseases, including condyloma acuminata or anogenital warts, intraepithelial neoplasia, and carcinoma of the penis and anus [2]. These diseases are associated with substantial morbidity and mortality [3]. In females, persistent genital HPV infection can cause cervical cancer, other types of anogenital cancers and genital warts [2].

This study intends to build on the large body of safety experience from the administration of GARDASILTM to females, including a large post-licensure observational safety study. In clinical trials involving the administration of GARDASILTM to young males, the vaccine was generally well tolerated. No serious adverse events have been identified to be associated with GARDASILTM in the randomized clinical trials involving over 3,000 young male recipients of GARDASILTM.

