#### 4.1.2 Relative Risks

Relative risks (RRs) will be calculated as the ratio of the incidence of the health outcome in the risk and self-comparison periods. Confidence intervals (CIs) will be calculated

Protocol/Amendment No.: 070-01

using the mid-probability exact method. Consistent with the primary and secondary objectives, RRs and CIs (along with number of events and incidence) will be calculated for the analyses shown in Table 4-1.

For health outcomes occurring in the risk period but not in the self-comparison period (or vice versa), incidence for the period with one or more events will be calculated but relative risks will not be provided. Number of events will be displayed for all prespecified HCUP categories of interest, even if no events occurred.

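### If vaccination dates cluster in the year, the unadjusted self-comparison relative risk is open to seasonal confounding, mainly for dose 1 and common seasonal outcomes

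*Protocol*

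**What the plan says.** Every general-safety analysis in Table 4-1 of the protocol uses self-comparison as its only comparator. Section 3.7.1 sets the timing: "The post-vaccination self-comparison period will start 91 days after each dose of" the vaccine, which leaves room for the 60-day risk period and a 30-day washout before the "start of up to 3 self-comparison periods, each up to 60 days in length". The footnote to Figure 3-2 gives an example in which "the post-vaccination self-comparison time is the combined time of month 5-6 and 9-14", for a vaccine given "according to the following schedule: 0, 2 and 6 months".

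Section 4.1.2 fixes the estimator: "Relative risks (RRs) will be calculated as the ratio of the incidence of the health outcome in the risk and self-comparison periods", with confidence limits obtained "using the mid-probability exact method". It names no calendar term, stratum or matching.

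Section 3.7.1 gives the reason for the design: "This means that whatever characteristics (both measured and unmeasured) are associated with receipt of the vaccine will be evenly distributed among the exposed and unexposed". Under Section 3.6.1 the outcomes are all diagnoses leading to an emergency room visit or hospitalization, grouped into HCUP categories.

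**The concern.** A male who serves as his own control balances whatever stays the same in him. He does not balance what changes between his two observation windows, and season is such a factor. For dose 1 the order of the windows is fixed and the comparison window comes later. If many males are vaccinated at the same time of year, their risk time falls in one season and their comparison time in the next. Any diagnosis category with a seasonal rate then has a relative risk that differs from 1 for a reason unrelated to the vaccine.

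The error can go either way. It can produce an apparent excess for the Safety Review Committee to chase, or cancel a real one. The multiplicity adjustment in Section 4.1.3 deals with chance findings and leaves a systematic shift in place. No concurrent comparator in the general-safety analyses would show the shift for what it is.

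**Working it through.** **Inputs from the protocol.** Risk time is days 1-60 after each dose and comparison time starts on day 91 (Sections 3.6.1 and 3.7.1). The schedule is 0, 2 and 6 months (Section 1.1). The accrual target is 135,000 initiators (Section 3.5). Table 4-2 covers background incidences from 1/2,000 to 1/20,000 per two-month window. The protocol has no figure for season, so there is none to reproduce.

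**Assumptions, which the protocol does not supply.** There is no vaccine effect. The outcome rate is proportional to 1 + a·cos(2π(day − peak)/365), with a = (r − 1)/(r + 1) for a peak-to-trough ratio r. Half of first doses fall in the 92 days of July-September, spread evenly, and half in the other 273 days.

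**Dose 1, days 1-60 against 91-150.**

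- Uptake is an even layer plus an excess in the quarter of 1 − 365 × 0.5/273 = 0.3315. Averaging the cosine over 92 days gives sin(92π/365)/(92·sin(π/365)) = 0.899. The seasonal strength of uptake is 0.3315 × 0.899 = 0.298.
- Averaging over a 60-day window gives sin(60π/365)/(60·sin(π/365)) = 0.956.
- For r = 2, a = 1/3, so the mean rate in each window moves by up to 0.333 × 0.298 × 0.956 = 0.095 around 1. The window centres are 90 days apart.
- The worst peak date on the high side is late July: risk 1.062, comparison 0.929, ratio 1.14. On the low side it is early February: 0.929/1.062 = 0.875, or 0.88.
- For r = 3, a = 0.5, and the same steps give 0.82-1.22.

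**Three on-schedule doses combined.** Doses are at days 0, 60 and 180, so risk time is days 1-120 and 181-240. Comparison time is days 151-180 plus either days 271-330 (the 60-day cap in Section 3.7.1) or days 271-420 (the Figure 3-2 example). Both are run because the two descriptions differ and need reconciling.

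| Analysis | 2:1 season | 3:1 season |
|---|---|---|
| Dose 1, days 1-60 vs 91-150 | 0.88-1.14 | 0.82-1.22 |
| Three doses, 60-day cap | 0.92-1.08 | 0.89-1.13 |
| Three doses, Figure 3-2 | 0.94-1.07 | 0.91-1.10 |
| Any layout, even uptake | 1.00 | 1.00 |

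Each range covers all possible peak dates.

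**Sensitivity to the uptake curve.** With a smooth curve that puts 37% of first doses in the busiest quarter, the dose 1 range at 2:1 is 0.90-1.11. With 49% it is 0.82-1.22, because that curve also thins out the opposite season.

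**Sensitivity to the window.** Days 91-150 are fully free only if dose 2 has not been given by then. If the on-schedule gap at days 151-180 is used instead, the same formula gives 0.84-1.20 at 2:1.

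**When it would be noticed.** For a 1 September peak at 2:1, the dose 1 ratio is 1.092/0.979 = 1.12. Assume a common category with background 1 per 200 per 60 days. Then 135,000/200 = 675 events per period, SE(ln RR) = √(2/675) = 0.054, and z = ln(1.115)/0.054 = 2.0. At the most frequent background in Table 4-2, 135,000/2,000 = 67.5 events, and z = 0.109/√(2/67.5) = 0.6. At 1/12,000 there are 11.25 events, and z = 0.26.

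The chance that a null category shows a nominally significant excess is about Φ(ln RR/√((1 + 1/RR)/n) − 1.96), where n is the number of comparison-period events. Without bias it is 2.5%.

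| Events per period | Spurious RR 1.1 | Spurious RR 1.2 |
|---|---|---|
| 11 | 4% | 7% |
| 50 | 7% | 16% |
| 200 | 16% | 48% |
| 1,000 | 59% | 99% |

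**Masking.** A seasonal factor of 0.88 would bring a true relative risk of 1.14 to 0.88 × 1.14 = 1.00.

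**The case against.** The strongest reply has four parts.

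1. The harm depends on facts the protocol does not give. It has no dose-date distribution and no seasonal rates, and with even uptake the bias vanishes. This stands, and the point is conditional on it.

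2. The primary analysis combines doses, and there the order is not fixed. In the Figure 3-2 example, the comparison time at months 5-6 comes before the dose 3 risk period, and months 13-14 repeat the calendar months of the first risk period: 55 of the 180 comparison days share a calendar date with risk time. A reader might infer from the 91-day rule that comparison time always lies in another season. The example contradicts that. Under the 60-day cap the shared dates disappear, but the interleaving remains. This stands, and it is why the combined-dose ranges are narrower.

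3. Statistical detail is left to the Data Analysis Plan, which is not shown and may contain a calendar adjustment. This stands in part. Section 4.1.2 already states the estimator and Section 3.7.1 already states the justification, and both can be judged as written. It would be wrong to conclude that no adjustment is planned anywhere.

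4. The study is descriptive, and the committee weighs plausibility, temporal relationship and clustering (Section 3.3). This tempers a false excess. It does nothing for a masked one, and season is not among the listed considerations.

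The sentence in Section 3.7.1 can also be read narrowly, because it concerns characteristics of the vaccinated and follows a claim only to reduce confounding relative to an external cohort. It is therefore incomplete rather than a claim about season.

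**Conclusion.** The point holds in a conditional form. As stated, the relative risk has no protection against season, and the justification in Section 3.7.1 reaches further than self-comparison can. If half of first doses fall in one quarter and the outcome has a 2:1 seasonal swing, the null relative risk for dose 1 can be anywhere from about 0.88 to 1.14, depending on when the outcome peaks. For three doses combined the range is about 0.92-1.08 or 0.94-1.07, depending on which layout of comparison time applies.

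This matters for dose 1 (Secondary Objective 1) and for common seasonal categories, where several hundred events per period make a shift of this size visible. It is unimportant for the rare outcomes on which Table 4-2 is built, where the study looks for relative risks of 2 to 5. A reader might infer that seasonal illness will produce false signals in this study. The documents do not support that, because nothing in them shows that vaccination dates cluster. Day 1-14 was not sized here: its comparator is tied to a physician visit and Section 3.7.1 leaves the method open.

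**What to change.** In Section 4.1.2, prespecify a relative risk stratified by calendar month, or by quarter where events are sparse, for the Day 1-60 analyses. Extend it to Day 1-14 once that comparator is settled. Report it beside the crude ratio, at least as a sensitivity analysis for the Safety Review Committee. Each male's risk and comparison person-time can be split by month from the dated claims already held. If vaccination is not seasonal, the two estimates will agree on average.

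In Section 3.7.1, limit the sentence on evenly distributed characteristics to those that do not change over time, and say that season is handled in the analysis.

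The cost is extra programming and a small loss of precision from stratifying. Very sparse categories will support only the crude ratio, but these are also the categories where the bias matters least.

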## 3.3 SAFETY REVIEW COMMITTEE (SRC)

An SRC that is external to the study will consist of independent experts in various relevant areas such as vaccine safety, immunology, pharmacoepidemiology, rheumatology, neurology, pediatric infectious diseases, or adolescent medicine. As much as possible, the SRC will consist of an odd number of voting members to avoid a tie in voting. In case of a tie, where the SRC consists of an even number of members, the SRC chair's vote will prevail. One of the SRC members will be selected as the chairperson in the first SRC meeting and will facilitate the subsequent meetings. The SRC chairperson will be selected by consensus among the SRC members.

The SRC will meet annually (or more often, if deemed necessary) to review data compiled by PPD in preparation for the annual interim reports and the final study report, and to assess any evidence that may be indicative of a potential signal. The assessment of safety will be made based on a process that is pre-specified in the SRC Standard Operating Procedures (SOP). The possible relationship of an event to GARDASILTM will be assessed by the SRC based on statistical and clinical judgment of a range of information elements, including biological plausibility, clinical relevance, statistical strength, adjustment for false discovery rate due to multiple comparisons, temporal relationship, and time distribution of the event after vaccination (i.e., the existence of a cluster or not).

If the SRC determines that the data suggest a potential safety signal, further investigations may be conducted, as requested by the SRC. The investigation can include, but may not be limited to, assessment of the existence of a cluster, additional exploratory data analysis (such as SaTSCAN analysis), or medical record review (for example, to determine if a condition was pre-existing prior to vaccination with GARDASILTM or to determine the nature of the condition resulting in a specific diagnosis code). In addition, the SRC may request case review or adjudication of diagnosis in the general safety portion of the analysis, if it identifies the need for additional information on certain general safety outcomes.

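### The self-comparison balances fixed traits, not other vaccines given at the GARDASIL visit, so the planned Day 0 and Days 1-14 RRs describe the vaccination visit rather than GARDASIL alone

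*Protocol*

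**What the plan says.** Section 3.7.1 makes each vaccinated male his own control. It argues that this reduces confounding relative to an external cohort, and concludes that "whatever characteristics (both measured and unmeasured) are associated with receipt of the vaccine will be evenly distributed among the exposed and unexposed groups".

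The comparison time is set as follows: "The post-vaccination self-comparison period will start 91 days after each dose of GARDASIL". For the short windows, Section 3.7.1 ties the comparator to a health care contact. For Day 0, "a day on which a doctor visit occurred during the self-comparison period will be used for outcome assessment for Day 0 analyses"; for Days 1-14, "the self-comparison period will be 14 days following the date associated with a physician visit if such visit occurred". Neither rule asks for a vaccination or an injection at that contact.

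Section 3.6.1 limits Day 0 to syncope, epilepsy or convulsions, head trauma and allergic reactions, chosen for "temporal and biological plausibility for an association with an injection or vaccination".

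Section 3.5 says that doses are given "as part of their routine medical care". Section 3.4.3 is inclusive ("As a general rule, all males vaccinated with at least one dose of GARDASIL") and lists no exclusion for other vaccines. Section 4.1.2 defines the RR as incidence in the risk period over incidence in the self-comparison period, for the analyses in Table 4-1. The protocol text does not mention other vaccines given at the same visit.

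**The concern.** A self-comparison removes confounding by whatever stays the same within a person, such as sex, genetics and long-standing health. It does not remove confounding by an exposure that comes and goes with the dose. Another vaccine given at the GARDASIL visit is such an exposure: it is associated with receipt of GARDASIL, it varies over time, and it starts on the same day. The sentence in Section 3.7.1, read as written, covers it and should not.

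The stake is interpretation. The objectives in Section 2 concern the safety of GARDASIL, and under Section 3.3 the SRC judges the possible relationship of an event to GARDASIL. If another vaccine, or the added injection, raises the risk of syncope or an allergic reaction, the planned RR rises even if GARDASIL adds nothing. Timing cannot tell the two apart, because they share day zero.

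**Working it through.** **1. Where a same-day vaccine falls.** Call the dose day 0.

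| Window | Time since a same-day vaccine | Vaccination required in the comparator? |
|---|---|---|
| Day 0 | 0 days | No; a doctor-visit day |
| Days 1-14 | 1-14 days | No; 14 days after a physician visit, if there was one |
| Days 1-60 | 1-60 days | No |
| Self-comparison | at least 91 days | - |

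A comparison visit may happen to include another vaccine, so the contrast is not all or nothing. But co-administration is aligned with the risk window by construction, and with comparison time only by chance.

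**2. The plan's own figures.** The protocol gives no figure for co-administration. The nearest is the power statement in Section 4.1.5: 50% and 92% for RR 2 and 3 at a background of 1 per 12,000, with 132,000 doses and two-sided alpha 0.05. Expected events in comparison time are 132,000/12,000 = 11, against 22 or 33 in risk time.

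- RR 2: z = (22 - 11)/√(22 + 11) = 1.915; power = Φ(1.915 - 1.960) = 48.2%.
- RR 3: z = (33 - 11)/√(33 + 11) = 3.317; power = Φ(3.317 - 1.960) = 91.3%.

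Both are within 2 points of the stated values. They show that RRs of 2 to 3 are the size the study is built to see.

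**3. Effect of co-administration on the RR.** Let q be the share of risk time with another vaccine, q0 the share of comparison time, and r the RR of that vaccine in the window. With a true GARDASIL RR of 1,

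observed RR = [1 + q(r - 1)] / [1 + q0(r - 1)].

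None of q, q0 or r is in the protocol; all are assumed.

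| q | r = 2, q0 = 0 | r = 2, q0 = 10% | r = 3, q0 = 0 | r = 3, q0 = 10% |
|---|---|---|---|---|
| 20% | 1.20 | 1.09 | 1.40 | 1.17 |
| 40% | 1.40 | 1.27 | 1.80 | 1.50 |
| 60% | 1.60 | 1.45 | 2.20 | 1.83 |

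Example: q = 60%, r = 3 gives 1 + 0.6 × 2 = 2.20; with q0 = 10% it is 2.20/1.20 = 1.83. Over a wider grid (q 20-80%, r 1.5-5, q0 0-10%) the result runs from 1.05 to 4.20.

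**4. What that could do to a table.** At q = 50%, r = 3, q0 = 0 the observed RR is 2.0. In the set-up of Table 4-2 (132,000 doses, equal risk and comparison time), a mid-p test would show a significant excess with probability of about 47% at 1/12,000, 85% at 1/5,000 and over 99% at 1/2,000, against about 2.5% with no effect. Table 4-2 uses a two-month background risk, and these probabilities are before any multiplicity adjustment. They give a sense of scale and do not carry over to Day 0.

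**The case against.** **The sentence is comparative.** The line before it says only that confounding is reduced relative to an external cohort, and the sentence itself speaks of characteristics of group members. The comparative claim is sound. The sentence as written is still broader than the design supports.

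**The detail belongs in the Data Analysis Plan.** The protocol calls Section 4 an overview and defers self-comparison details to that plan, which is not shown and may stratify by same-day vaccines. This stands. A reader might infer that the study has no analysis for co-administration; the documents do not allow that conclusion. The point rests on the sentence and on the contrast that the protocol itself fixes.

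**The SRC will catch it.** A reader might infer that a raised RR would simply be credited to GARDASIL. Section 3.3 does not support that: the SRC uses "statistical and clinical judgment of a range of information elements, including biological plausibility, clinical relevance, statistical strength" and further elements, in a list that is open-ended, and it may request medical record review. Co-administration is unnamed, not ruled out. Without the share of doses affected, however, the SRC has no figure to weigh.

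**Routine use is the question.** The study is descriptive and set in routine practice (Section 2.3), so an all-doses RR is a legitimate target. This stands, and that RR should remain primary.

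**The illustration is one-sided.** It treats GARDASIL as inert and the other injection as harmful. If both act and their effects multiply, the same factor multiplies the GARDASIL RR. If a second injection adds nothing to the first, there is little or no inflation. Section 3.6.1 states plausibility for Day 0 outcomes only. It does not say that a co-administered vaccine causes them, and it does not extend that rationale to later windows.

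**Conclusion.** The balance sentence in Section 3.7.1 is overstated, and the Day 0 and Days 1-14 RRs as planned estimate the effect of the vaccination visit rather than of GARDASIL alone. That follows from the protocol's own window and comparator rules and needs no assumed figure.

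The size does need assumptions. With an other-vaccine RR of 3 and no GARDASIL effect, the observed RR is 1.4 to 2.2 at 20-60% co-administration when comparison time has none; 10% in comparison time lowers the top value to 1.83. With few co-administered doses or a weak co-vaccine effect the distortion could be trivial.

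Two stronger readings are not supported. One is that GARDASIL and other vaccines cannot be separated at all. The limit lies in the planned contrast, since vaccination dates and procedure codes are in the claims (Sections 3.1 and 3.5). The other is that every row of Table 4-1 needs a second version. The case is strongest for Day 0, reasonable for Days 1-14, and not made for Days 1-60.

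**What to change.** - In Section 3.7.1, limit the balance sentence to characteristics that do not change over time, and say that exposures tied to the vaccination visit, such as same-day vaccines, are not balanced.
- Keep the all-doses RR as primary.
- For the Regimen Initiator Day 0 and Days 1-14 rows of Table 4-1 (all doses combined and dose 1, so four rows), add a supportive RR restricted to doses with no claim for another vaccine on the same day. Use comparison visits that also have no vaccine claim that day.
- If vaccines given later in the window are to be handled, censor person-time at that vaccine and do not drop the dose. Dropping it selects on later exposure: if an emergency visit or admission delays the next vaccine, doses with events are kept more often and the RR is inflated.
- Report the share of doses with a same-day vaccine to the SRC.

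Cost: a same-day vaccine flag from claims already held, applied to doses and comparison visits, and four supportive analyses. The restricted analyses will have fewer events and wider intervals, they add a few comparisons to an already long list, and vaccines given outside the health plan will be missed.
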